#### 3.1 Inclusion Criteria

- All participants must have signed an informed consent document indicating they understand the purpose of the study and the procedures required for the study and are willing to participate by complying with the study procedures and restrictions.
- 2. Male or female individuals of any race; between 18 to 60 years of age, inclusive.
- 3. Resides in a stable living situation, according to the investigator's judgment.
- 4. Diagnosis of bipolar disorder I or II for at least 1 year in duration, as established by the SCID-I, and verified with medical records and/or confirmation of diagnosis by treating clinician. Patients will be in a nonacute phase at the time of initial screening and have been so for at least 1 month.
- 5. No more than moderate clinical symptom burden severity, as defined by the following:
  - Montgomery Asberg Depression Rating Scale ≤ 20
  - Young Mania Rating Scale ≤12
- 6. Individuals medically stable enough to complete an 8 week clinical trial, in the judgment of the investigator

- 7. Women of childbearing potential must have a negative pregnancy serum test at screening, negative pregnancy urine test at baseline, and agree to use adequate protection (i.e. double barrier method) for birth control.
- 8. Antidepressant (AD) medications are allowed if the subject has been treated with a stable dose for at least 2 months before screening.
- 9. Individuals receiving a single mood stabilizer (e.g., lithium. valproate, or lamictal) are allowed if a stable dose has been maintained for at least 2 months prior to screening.
- 10. Individuals may be receiving one treatment of each the following groups: antidepressants, mood stabilizers, and atypical antipsychotics other than clozapine, but not more than one from each group.
- 11. Individuals taking ripseridone, lurasidone, or ziprasidone must be currently taking solder: doses of 3mg, 40mg, and, 80mg, respectively.
- 12. Subjects may be treated with inclusionary antipsychotic drugs as long as they are on a stable dose of injectable medication for 2 months or a sable dose of an oral medication for 1 month. Exclusionary antipsychotic drugs are listed in Appendix 2.
- 13. Patients with a history of compliance with a drug treatment regimen for bipolar disorder, as noted in medical/psychiatric history.
- 14. CNS stimulants (e.g., Adderall, Ritalin) are permitted if the participant is stable on their dosage of medication for 1 month before screening and cannot change dosage throughout the study.
- 15. Able to complete cognition assessments in English
- 16. Individuals must demonstrate a substantive cognitive deficit, as measured by the Trails A, Hopkins Verbal Learning Test (HVLT), and the Letter Number Span, administered at the screening visit. Eligible individuals will have an established cognitive deficit as measured by one or more of these tests, scoring below the 75th percentile, using comparative norms according to age, gender, and education.
- 17. Able to understand and complete cognition assessments

#### 3.2 Exclusion Criteria

- 1. Failure to perform screening or baseline examinations
- 2. Hospitalization within 8 weeks before screening, or change in mood stabilizing or antidepressant medication or dose within 2 months prior to screening
- 3. Individuals who have participated in another clinical study within the past 2 months.
- 4. Individuals with tardive dyskinesia.
- 5. Individuals with other DSM-V Axis I or Axis II primary diagnoses.

- 6. Diagnosis of alcohol or substance use disorder within the past 3 months.
- 7. Subject assessed to be at significant suicide risk based on responses to the Columbia Suicide Severity Rating Scale (C-SSRS).
- 8. History of myocardial infarction, unstable angina, uncontrolled hypotension or hypertension within 3 months before screening.
- 9. Clinically significant abnormality on screening ECG.
- 10. Alanine transaminase (ALT) or aspartate transaminase (AST) > 2.5 times the upper limit of normal (ULN).
- 11. History of stroke, brain tumor, head trauma with loss of consciousness, or other clinically significant neurological condition within 12 months before screening.
- 12. Individuals with other uncontrolled medical conditions, in the opinion of the investigator.
- 13. Use of drugs known to be metabolized by CYP2D6 (see Appendix 2)

## 4.0 Study-Wide Number of Individuals

4.1 There will be 60 total participants

## 5.0 Study-Wide Recruitment Methods

5.1 This is a multi-center study. We will be using referrals directly from the providers and recruitment materials by posting in the clinics. We will utilize referrals from primary care or psychiatry providers, or from participant interest and consent. We will also be recruiting individuals through the NU-SRG Recruitment Pipeline (STU00059328) for the Northwestern University site.

#### 6.0 Multi-Site Research

6.1 This is a multi-center study. There are two study sites where the research procedures will take place: Northwestern University, Chicago, IL and Beacon Medical Group Behavioral Health South Bend, South Bend, IN. Northwestern University will be the coordinating center and Beacon Medical Group Behavioral Health South Bend will be a satellite site.

## 7.0 Study Timelines

#### Schedule of Assessments:

Study Day	Screen	1	7	14	21	28	35	42	49	56	84
Event/Assessment					Phone Call		Phone Call		Phone Call		Phone Call
Informed Consent	Х										
Medical History &											
Demographics	X										
Physical Examination	X										
Electrocardiogram	Х					Х				Х	
Vital Signs	Х	Х	Х	Х		Х		Х		Х	
Clinical Safety Laboratory Tests	х					Х				х	
Serum Pregnancy Test	Х										
Urine Pregnancy Test		Х									
Urine Drug Screen	Х										
Inclusion/Exclusion Criteria	х										
SCID-I	Х										
Screening neurocognitive assessments	x										
Montgomery Asberg Depression Rating Scale		Х				X				x	
SLOF		х								x	
C-SSRS	Х	Х	Х	Х	Х	Х	Х	Х	Х	Х	X
AIMS		Х				Х				Х	
Neurocognitive battery	Х	Х								Х	
CGI-BP		Х				Х				Х	
Young Mania Rating Scale		х				Х				х	
Assessment of Concomitant Medication	х	х	х	х	х	х	х	Х	х	х	X
Assessment of Adverse Events	X	х	X	X	x	X	X	X	х	X	х

# 8.0 Study Endpoints

The declarative verbal memory subscales will be the primary endpoints. Secondary outcome measures will include cognition composite score, the MADRS total score (for those with a MADRS score between 8 and 20 at the time of enrollment) and individual scores for each of the other neuropsychological tests. We will assess JNJ-18038683 effects on functional ability and clinical global severity scores as additional endpoints, as measured by the SLOF and CGI-BP. Further, we will analyze the effect on drug tolerability as determined by the following: body weight, body mass index (BMI), waist circumference, and movement rating scales.

#### 9.0 Procedures Involved

Study visits will include screening and 6 visits (baseline, Weeks 1, 2, 4, 6, and 8). Please see Appendix 1 – Schedule of Assessments

At screening, the Structured Clinical Interview for Diagnosis for DSM Disorders (SCID) will be completed for confirmation of psychiatric diagnosis. A medical/psychiatric history will also be collected and a physical exam will be performed. Vital signs including weight, height, waist and hip measurement will be obtained at screening to record body mass index. The Hopkins Verbal Learning Test (HVLT) and Trail Making Test A (TMT-A), will be administered to screen for severity of cognitive impairment. Only individuals who score between the 25th and 75th percentile as compared to normative data on these tasks will be enrolled.

If the subject is determined eligible during the screening procedure, which can last for up to two weeks, a baseline visit will be scheduled. Baseline assessments of cognitive function, psychopathology and global function will be administered along with movement ratings at the baseline visit. Functional outcome will be assessed with Specific Level of Function Scale (SLOF) [33]. Adverse events will be collected and recorded from the time the subject signs the informed consent to the final safety follow-up visit, and motor side effects will be monitored by the Abnormal Involuntary Movement Scale at the following visits: baseline, Weeks 4 and 8.

Individuals will be randomized to receive JNJ-18038683 or placebo after the completion of the baseline assessments. Individuals will be stratified for randomization as either being treated with an AD or not being treated with an AD. As in the previous study of JNJ-18038683 for depression, individuals randomized to JNJ-18038683 will receive 10 mg for one week, then titrate to 20 mg, with the provision for a single, downward dose adjustment for intolerance, based upon investigator judgment. No antipsychotic drugs which are 5-HT7 antagonists will be permitted to avoid effects upon 5-HT7 receptors from enhanced 5-HT concentrations and possible down regulation of 5-HT7 receptors. As JNJ-18038683 is a competitive inhibitor of CYP2D6, there will be a 2 week washout period requested after the trial prior to initiation of any CYP2D6 substrates (see Appendix 2).

Individuals will be asked to return to the clinic at study weeks 1, 2, 4, and 6 after baseline to monitor for side effects and compliance. At the Week 4 visit, efficacy assessments will be completed (MADRS, YMRS and CGI-BP). Between clinic visits, research staff will complete phone calls with individuals at study Weeks 3, 5, and 7. Individuals will return for a final study visit 8 weeks after initiation of the randomized study medication. A Safety Follow-up phone call will take place 4 weeks after the final visit and safety assessments will be completed (C-SSRS, Adverse Events, Concomitant Medications). The assessments completed at baseline will be repeated at this Week 8 visit (See Appendix 1 – Schedule of Assessments). Reasons for early termination will be recorded. Every effort will be made to obtain appropriate rating scale data at the final visit of early terminators.

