#### 2.2 Rationale for Randomized Controlled Trial of JNJ-18038683 on Cognition and Residual Depressive Symptoms in Bipolar Disorder

Based on the pre-clinical, pro-cognitive effects of 5-HT7 antagonism in our laboratory, along with the reported pre-clinical antidepressant effects of JNJ-18038683, we propose to conduct a randomized, placebo-controlled parallel, design study to assess the effects of JNJ-18038683 on multiple domains of cognition and mood symptoms. Since our preclinical studies show that 5-HT7 receptor blockade is highly effective in improving declarative memory in rodents. the declarative memory measures will be the primary outcome measures. As previously discussed Andressen et. al [39] noted differential functional selectivity of the 5-HT7 receptor, suggesting that the effects of atypical APDs with known 5-HT7 antagonism, such as lurasidone, ziprasidone and risperidone, are modulated via different HTR7 subunits than JNJ1083868. In light of this new information, we proposed to allow some individuals currently prescribed treatment with atypical APDs with 5-HT7 antagonism to be eligible for screening and randomization.

Due to the effect of JNJ-18038683 on depressive symptoms in preclinical paradigms [12], we will investigate the following in the clinical trial the potential antidepressant effect of JNJ-18038683 on patients with baseline MADRS score between 8 and 20.

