#### 3.0 Inclusion and Exclusion Criteria

All patients will meet criteria for DSM-V diagnosis of Bipolar I or Bipolar II disorder. At the time of enrollment, patients will be relatively stable, and may be in a mild-moderate depressed state. 60 patients will be enrolled, and randomized in a 1:1 ratio to one dose of JNJ-18038683 or placebo. Randomization will be stratified by the presence / absence of atypical APDs with 5-HT7 antagonism so that there is a balance in the assignment of active treatment and placebo in individuals who are, and are not, receiving atypical APDs with 5-HT7 antagonism. The percentage of those enrolled that are prescribed these atypical APDs will be 35% of the overall enrollment.

Individuals must meet all of the inclusion and exclusion criteria to be registered to the study. Study treatment may not begin until a subject is registered.

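### The protocol contradicts itself on cognitive entry, permitted antipsychotics and the stratification factor, and the SAP does not name the randomisation scheme that replaced the intended one

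*Protocol*

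**What the plan says.** **Cognitive entry.** Protocol Section 3.1, criterion 16, uses Trails A, the HVLT and Letter Number Span. One qualifying score is enough: "scoring below the 75 th percentile, using comparative norms according to age, gender, and education". There is no lower limit. Section 9.0 names only the HVLT and Trails A, refers to normative data without further detail, and states: "Only individuals who score between the 25 th and 75th percentile as compared to normative data on these tasks will be enrolled".

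**Antipsychotics.** Section 2.2, citing newer receptor evidence, says "we proposed to allow some individuals currently prescribed treatment with atypical APDs with 5-HT 7 antagonism to be eligible for screening and randomization". Section 3.0 adds: "The percentage of those enrolled that are prescribed these atypical APDs will be 35% of the overall enrollment". Criterion 10 allows "atypical antipsychotics other than clozapine, but not more than one from each group". Criterion 11 names risperidone, lurasidone and ziprasidone as drugs a participant may be taking, and Appendix 2 does not list those three as prohibited. Section 9.0 says the opposite: "No antipsychotic drugs which are 5-HT 7 antagonists will be permitted".

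**Randomisation.** Section 3.0: "Randomization will be stratified by the presence / absence of atypical APDs with 5-HT 7 antagonism". Sections 9.0 and 9.2 both stratify by antidepressant treatment, and 9.2 adds permuted blocks. The SAP (Goals) describes the antipsychotic scheme as the initial intention and reports that recruitment difficulties led to a change. It gives neither the new scheme nor a date.

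**Primary model.** Protocol Section 11.1 adjusts for baseline, sex and race. The SAP (Primary analysis for efficacy) adjusts for baseline and age, and will examine MADRS, YMRS and global severity. Neither names antipsychotic or antidepressant use. The SAP's secondary section mentions concomitant medication, but only generically and as exploration.

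**The concern.** All of this is current operative text. A site cannot follow both versions of the entry rule or both versions of the antipsychotic rule. A reader of the final report could not tell from these documents how participants were allocated.

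Two different things are at stake. The entry and medication rules define the population: whether the most impaired patients are in or out, and whether about a third of participants take drugs that act at the study drug's own target. The stratification factor defines the allocation, and the usual analysis adjusts for whatever factor was used. That cannot be written down while the factor is unknown.

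**Working it through.** **The plan's own figure.** Section 11.1 gives SD 9.4, correlation 0.5, two time points and a difference of 5. The variance of the time-averaged score is 9.4² × (1 + 0.5)/2 = 66.27 (SD 8.14).

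- One-sided: n = 2 × (1.645 + 0.842)² × 66.27 / 25 = 32.8, so 33 per group (power 0.802).
- Two-sided: n = 2 × (1.960 + 0.842)² × 66.27 / 25 = 41.6, so 42 per group.

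Both match the protocol. They do not bear on the contradictions. The ANCOVA residual variance, 9.4² × (1 − 0.5²), is also 66.27 and is used in step 3.

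**Step 1: entry rules side by side.**

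| | Criterion 16 | Section 9.0 |
|---|---|---|
| Tests | Trails A, HVLT, Letter Number Span | HVLT, Trails A |
| Upper limit | 75th percentile | 75th percentile |
| Lower limit | none | 25th percentile |
| Logic | one or more tests | not stated whether both or either |
| Norms | age, gender, education | not specified |

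A patient below the 25th percentile on both the HVLT and Trails A can be eligible under criterion 16 and is barred by Section 9.0 on either reading of its logic.

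To illustrate how far the rules diverge, I simulated three normal scores with common norms, cut-offs at ±0.674, and assumed inter-test correlations of 0, 0.5 and 0.7. The percentages classified differently were:

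| Assumed mean deficit | Both tests must be in band | One test suffices |
|---|---|---|
| 0 SD | 73 / 65 / 58 | 23 / 20 / 20 |
| 0.5 SD | 80 / 74 / 69 | 30 / 32 / 34 |
| 1 SD | 89 / 84 / 81 | 46 / 50 / 52 |

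The documents fix neither the correlations nor the deficit in this population. Section 2.1.1 cites deficits of 1.2 SD (speed of processing) and 1.8 SD (verbal learning), but in treatment-resistant inpatients.

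**Step 2: antipsychotics.** Section 3.0 implies 0.35 × 60 = 21 participants on 5-HT7-antagonist antipsychotics. Section 9.0 implies 0.

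**Step 3: leaving out a stratification factor that was used.** Suppose a fraction p of patients has the factor and it shifts the outcome by δ. Its variance is v = p(1 − p)δ². Stratification balances the factor, so the true residual variance is 66.27 − v, while the model that omits it estimates 66.27. With 30 per arm and a normal approximation:

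- alpha = 2Φ(−1.96 × √(66.27/(66.27 − v)))
- SE₀ = √(2 × 66.27/30) = 2.10 and SE₁ = √(2 × (66.27 − v)/30)
- power if omitted = Φ((5 − 1.96 × SE₀)/SE₁); power if included = Φ(5/SE₁ − 1.96)

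p = 0.35 comes from Section 3.0; p = 0.50 is assumed. The factor effect is assumed to be 0.2 to 0.5 SD, so δ = 1.88 to 4.70. If the factor also shifts the baseline score, a correlation of 0.5 lets the baseline term absorb half, leaving δ = 0.94 to 2.35.

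| p | δ | v | alpha | power omitted / included |
|---|---|---|---|---|
| 0.35 | 1.88 | 0.80 | 0.0486 | 0.663 / 0.668 |
| 0.35 | 4.70 | 5.03 | 0.0415 | 0.668 / 0.697 |
| 0.50 | 4.70 | 5.52 | 0.0406 | 0.669 / 0.700 |
| 0.35 | 0.94 | 0.20 | 0.0497 | 0.663 / 0.664 |
| 0.50 | 2.35 | 1.38 | 0.0476 | 0.664 / 0.672 |

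Alpha stays at or below 0.05 throughout. The two-sided power cost is about 0.1 to 3.1 points, and the one-sided cost is smaller (about 0.1 to 2.1).

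**The case against.** The strongest objection concerns the antipsychotics. Section 2.2 explains why the rule changed, and Section 3.0, criteria 10 to 12, Appendix 2 and the SAP all fit that change. One sentence in Section 9.0 does not. It is probably unrevised text, so this is less an even conflict than a leftover. That stands, though the sentence still has to be reconciled.

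It can also be said that Section 3 governs, since "Individuals must meet all of the inclusion and exclusion criteria to be registered to the study", and that the principal investigator approves every enrollee (Section 21.0). This makes divergence between sites less likely. It does not settle the cognitive rule, because a patient can meet every Section 3 criterion and still fail the additional restriction in Section 9.0. Likewise, the antidepressant scheme in Section 9.2 may well be the replacement, but neither document says so and Section 3.0 still carries the other factor.

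Three stronger readings are tempting and are not supported:

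- A reader might link the medication conflict to the SAP's remark that concomitant medications caused most screen failures. The SAP does not say which drugs. Exclusion 13, the long lists in Appendix 2 and the dose-stability rules offer ample other explanations.
- A reader might take the Section 9.0 rule to be a strict subset of criterion 16. That holds only if both use the same norms, and Section 9.0 does not specify its norms.
- A reader might infer biased treatment estimates or inflated type I error. Entry rules apply before randomisation, and omitting a balanced factor errs on the conservative side. The SAP reports a changed scheme, not non-random allocation.

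**Conclusion.** The contradictions are real and should be fixed. On cognitive entry the two rules differ in tests, floor, logic and possibly norms. On antipsychotics the implied number is 21 or 0, with the weight of the text on the permissive side. Both matter for whom the result applies to, not for the validity of the comparison between arms. On randomisation the documents leave the allocation method undefined, which is the more serious gap in reporting.

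The numerical consequence for the primary test is minor: at most slight conservatism, within the alpha and power ranges above, and only if a stratification factor was used and left out. Those ranges rest on assumed factor effects and on how much of the effect baseline absorbs. The entry-rule disagreement rates (about 58 to 89% if both tests must be in the band, 20 to 52% if one suffices) are illustrations under assumed normality, common norms, correlations of 0 to 0.7 and deficits of 0 to 1 SD. They are not estimates for this trial.

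**What to change.** **(a) Eligibility.** Reconcile criterion 16 with Section 9.0 on the tests, percentile limits, norms and whether one or both tests must qualify. Reconcile Section 9.0 with Sections 2.2, 3.0, 3.1 and Appendix 2 on antipsychotics. Record which rule was applied and from what date. This review does not choose the rule.

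**(b) Randomisation.** Before unblinding, state in the SAP each scheme actually used: stratification factor or none, block structure, start and end dates, and number randomised under it. Bring Sections 3.0, 9.0 and 9.2 into line with that statement.

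**(c) Primary ANCOVA.** For each primary test, add the factor or factors by which randomisation was actually stratified, alongside the covariates already planned. First reconcile the protocol's baseline, sex and race with the SAP's baseline and age, so that none is dropped by silence. If schemes were used in sequence, include each factor for all patients from baseline medication records, plus an indicator for the scheme period. If no factor was used, add no term.

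**Cost.** Wording in both documents and about 1 to 3 degrees of freedom: one for a single factor, three for two factors and a period indicator. The SAP describes conduct partly in the past tense, so items (a) and (b) may document what was done rather than change it.

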#### 9.1 Outcome Measures:

- A) Comprehensive cognition battery (measuring executive functioning, speed of processing, attention/vigilance, working memory, verbal learning, visual learning, reasoning and problem solving)
- B) Montgomery Asberg Depression Rating scale
- C) Young Mania Rating Scale
- D) Clinical Global Impression BP
- E) Columbia Suicide Severity Rating Scale
- F) AIMS scale for tardive dyskinesia
- G) Specific Level of Functioning
- H) Weight, height, waist circumference, triglycerides, FBS, LFTs

#### 9.2 Randomization Method:

Those who meet the study inclusion criteria will be randomized into one of two treatment groups, one to receive adjunctive therapy of JNJ-18038683 and the other to receive placebo. Individuals will be stratified for randomization as either being treated with an AD or not being treated with an AD. Using SAS software, a computer-generated randomization sequences for each treatment arm will be assigned using permuted block method limiting imbalance in numbers between groups. To assign the randomization, the SAS procedure PROC PLAN will be used [34]. Until the trial is concluded, the randomization sequence will be blind to the study participants as well as the Principal Investigator, research coordinators and raters. Randomization list will be provided by assigned statistician, [name], and will be held by unblinded study drug manager at [name] and at [name] for the Beacon Medical Group Behavioral Health South Bend site.

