## 11.0 Data and Specimen Management

#### 11.1 Data Analysis Plan

The primary analysis will be a mixed model repeated measures ANCOVA adjusting for baseline differences in dependent measures, sex and race. Missing data will be imputed by MMRM. We would also examine some variables categorically.

Assumptions for the power analysis included random assignment into one group receiving placebo and one JNJ-18038683. The cognitive battery, as the primary instrument, will be collected at baseline and at end point (8 weeks). Using repeated measure ANCOVA, the time average difference in the response variable will be compared between groups to detect treatment difference. Based on Javitt et al, 2012, we assume the mean baseline verbal learning score will be 36.2, SD 9.4 for both groups. We are assuming the placebo group will show no improvement while the treatment group will improve a mean of 5 points, a medium effect. We assume the correlation coefficient of repeated observation to be 0.5 and the covariance structure to be compound symmetry. The power calculation was conducted with alpha level of 0.05 using one-sided and two-sided tests. Full results are available upon request. With a one sided test, 33 individuals per group are required assuming 5 points improvement of the treatment group compared to the placebo for the desired power of 80% with alpha level of 0.05. We plan to recruit 36 per group to account for drop outs. In the two sided test the sample size per group is 42.

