Data Analysis Plan for Northwestern- Janssen R&D Collaboration Study

Protocol Title: Testing the ability of JNJ-18038683, a selective serotonin (5-HT)7 antagonist, to

improve cognition and reduce residual depressive symptoms in stable bipolar patients

Protocol Identifier Number: 18038683BCD2001

Northwestern University IRB Number: STU00200919-MOD0042

Version: 1.13

Date: 08.04.2021

Goals:

The goals of this study are to evaluate the efficacy of JNJ-18038683 in an 8-week trial to ameliorate the cognitive deficit and reduce residual depressive symptoms in 60 stable bipolar outpatients receiving treatment for depression. JNJ-18038683 will be studied and compared with placebo as adjunctive treatment to standard pharmacologic treatment for bipolar disorder. Sixty patients will be enrolled and randomized with a 1:1 ratio to one dose of JNJ-18038683 or placebo providing 30 subjects for each treatment arm. The initial intention was to follow stratified randomization based on the presence/absence of atypical APDs with 5-HT7 antagonism so that there is a balance in the assignment of active treatment and placebo in individuals who are and are not, receiving atypical APDs with 5-HT7 antagonism. However, due to recruitment difficulties, the stratified randomization method was not able to be followed as anticipated and was amended.

Assessments and Events:

Demographics, medical history, physical examination, serum pregnancy test, urine drug test, SCID-I diagnosis, and screening neurocognitive assessments will be done only during the screening visit. Urine pregnancy testing is performed at the baseline visit.

Table 1: Assessments completed during the screening visit only

Event /Assessment	Screen
Medical History & Demographics	X
Physical Examination	X
Serum Pregnancy Test	X
Urine Drug Screen	X
Inclusion/Exclusion Criteria	X
SCID-I	X
Screening neurocognitive assessments	X

Neurocognitive battery will be the primary measure of interest and evaluated at baseline and 8 weeks. The clinical global severity scores (CGI-BP), Young Mania Rating (YMRS), Scale for Tardive Dyskinesia (AIMS), Montgomery Asberg Depression Rating Scale (MADRS), Electrocardiogram and Clinical Safety Laboratory Tests will be collected at screening or baseline, and at 4 and 8 weeks. A measure of functional ability (SLOF) also will be assessed at baseline and 8 weeks. The schedule of these assessments is listed in table 2.

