The primary outcome measure for this study is verbal fluency performance as assessed with the Rey Auditory Verbal Learning Test, Rey Verbal Learning Test – Recognition Form, Verbal Fluency Test "Letterforms", and Animal Naming Test. The 8-week evaluation of verbal fluency after randomization is the primary outcome measure. Since the main interest is to measure the treatment effect for verbal fluency improvement from baseline and there is only one follow-up time point for the primary outcome variable, an ANCOVA model will be best suited for this study to compare the treatment effect using baseline value as a covariate. Alternatively, an ANOVA model will be used to compare the percent improvement and changes in the verbal fluency scores across treatment groups. Also, we plan to compare the treatment effect on verbal fluency performance over time using a mixed model. The missing evaluations will be imputed with the last value carried forward method, while model fit statistics will be used to estimate the appropriate covariance structure for this model.

There is both preclinical and clinical evidence that age has an important influence on 5-HT7 receptor function, which is the target of JNJ-18038683. Capacity to respond to JNJ-18038683 may decline with age. Thus, we predict the age of the subject will be related to the extent of improvement in verbal fluency and other measurements in the cognition battery. The relationship of age and percent improvement and the direct change of verbal fluency from baseline to 8 weeks in each treatment arm will be assessed using correlation analysis. The age variable will be used as a continuous variable in the analysis. If the distribution of the age variable is skewed, then age groups will be formed appropriately. In the above described ANCOVA and repeated measures models, age will be use as a covariate to assess the treatment effect. Graphical methods will be used to check for any inflection points of improvement of verbal fluency score in the treatment group compared to placebo. In the treatment group, better improvement is expected in younger patients compared to older patients. This relationship is not expected in placebo-treated patients. Additionally, with the above-mentioned models, the effect of covariates, MADRS total score, YMRS and Clinical Global Severity score on cognition will be examined because baseline mania or depression severity may influence performance on cognitive testing.

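### Two sites with staff-administered or staff-rated outcomes, but site is neither a stated randomisation stratum nor a term in any planned model

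*Protocol*

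**What the plan says.** **Sites.** Protocol section 6.0: "There are two study sites where the research procedures will take place". One is the coordinating university centre and the other a satellite.

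**Randomisation.** Three places bear on the strata, and none names site.
- Section 9.2 (and 9.0) uses antidepressant treatment: "Individuals will be stratified for randomization as either being treated with an AD or not being treated with an AD".
- Section 3.0 uses antipsychotics with 5-HT7 antagonism: "Randomization will be stratified by the presence / absence of atypical APDs".
- The SAP, under Goals, refers to the antipsychotic scheme and reports that "the stratified randomization method was not able to be followed as anticipated and was amended". It does not describe what replaced it.

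Section 9.2 says that sequences were "assigned using permuted block method limiting imbalance in numbers between groups". It has the list held by an unblinded drug manager, with a separate holding place "for the Beacon Medical Group Behavioral Health South Bend site". It does not say whether each site had its own blocked sequence.

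**Models.** Protocol section 11.1 plans a repeated-measures ANCOVA "adjusting for baseline differences in dependent measures, sex and race". For the primary analysis the SAP states that "an ANCOVA model will be best suited for this study to compare the treatment effect using baseline value as a covariate". It adds age, then examines MADRS, YMRS and global severity. Its secondary analyses explore gender, race, laboratory values and concomitant medication. Site is in none of these.

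**Outcomes.** The cognitive battery is administered at baseline and at the end of the study (9.4.2), the MADRS is a structured interview (9.4.3) and the SLOF is clinician-rated (9.4.7).

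**The concern.** Scores that depend on who gives the test or conducts the interview can differ between sites, as can case mix. Section 5.1 gives the coordinating site a recruitment route in addition to the referrals and postings used for the study as a whole. If site is neither balanced by design nor in the model, two things follow.

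- Any site difference that baseline does not explain stays in the residual variance.
- If one arm has more satellite patients than the other, part of that difference is included in the estimated treatment effect for this trial.

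What is at stake is precision, and how easily a result can be defended if the arm-by-site table turns out uneven. At 30 per arm the trial has little precision to spare. Site is known for every patient, so leaving it out saves no data collection.

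**Working it through.** **1. The plan's own figure.** Inputs from section 11.1: difference 5, SD 9.4, correlation 0.5, two time points, compound symmetry.
- Effective SD = 9.4 × √((1 + 0.5)/2) = 8.14.
- One-sided alpha 0.05 gives 33 per group with power 0.8024 (protocol: 0.80235). Two-sided gives 42 per group, as stated.
- ANCOVA on the Week 8 score has the same residual SD: 9.4 × √(1 − 0.5²) = 8.14.
- At the 30 per arm of section 22.0, power is 76.9% one-sided and 66.2% two-sided, and the standard error of the treatment difference is 8.14 × √(2/30) = 2.10 points.

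**2. What baseline adjustment does.** For a site difference that is equal at both visits, ANCOVA leaves the fraction 1 − 0.5 = 0.5. In the SAP's change-score ANOVA it cancels. For a difference that appears only at Week 8, neither removes anything.

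**3. Chance of an uneven split.** The satellite's share is not in the documents, so it is assumed. With 30/30 arms and allocation unrelated to site, the hypergeometric two-sided probabilities are as follows. The shift equals the residual site difference × the difference between arms in satellite share, for an assumed residual difference of 0.3 to 0.8 SD (2.82 to 7.52 points).

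| Satellite patients | Split at least as uneven as | Probability | Difference in share | Shift at that split |
|---|---|---|---|---|
| 10 | 7:3 | 0.299 | 4/30 | 0.38 to 1.00 |
| 15 | 10:5 | 0.233 | 5/30 | 0.47 to 1.25 |
| 20 | 14:6 | 0.054 | 8/30 | 0.75 to 2.01 |

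For the 10:5 case, 0.47 to 1.25 points is 9% to 25% of the assumed 5-point effect, and 0.47/2.10 = 0.2 to 1.25/2.10 = 0.6 of a standard error. If the site difference is stable, a residual of 0.3 to 0.8 SD requires a raw difference of 0.3/0.5 = 0.6 to 0.8/0.5 = 1.6 SD. A stable raw difference of 0.5 SD would leave 0.5 × 0.5 × 9.4 × 5/30 = 0.39 points.

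**4. Effect on precision, averaged over all splits.** With 15 satellite patients, the SD of the between-arm difference in share is √(15 × 45/59)/30 = 0.113. Multiplied by 2.82 to 7.52 points, this gives 0.32 to 0.85 points. The standard error rises from 2.10 to √(2.10² + 0.32²) = 2.13 at the low end and √(2.10² + 0.85²) = 2.27 at the high end, or about 1% to 8%.

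**5. Simulation.** Week 8 ANCOVA, 60 patients, two-sided 5%, satellite share 20% or 40%, 3,000 runs per cell.
- Without site in the model, mean bias was about 0 and type I error was 4.3% to 5.6%.

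| Assumed site difference | Change in power from adding site (percentage points) |
|---|---|
| None | −0.6 to −0.8 |
| 0.5 to 0.8 SD, stable | −1.1 to +1.9 |
| 0.5 SD, Week 8 only | +1.5 to +1.9 |
| 0.8 SD, Week 8 only | +3.9 to +6.8 (from 57–58% to 62–64%) |

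With 3,000 runs, differences of a point or so are partly simulation noise.

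**The case against.** The strongest reply is that this is a matter of efficiency and not of validity. Under randomisation, chance site imbalance averages to zero and the residual error reflects the added variance. The simulation bears this out. Both primary models already use the patient's own baseline, so a steady difference between examiners is halved, and it disappears from change scores. The 0.3 to 0.8 SD range is an assumption that no passage supports, and even then the shift is a fraction of one standard error. All of this stands.

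Some of the circumstantial support is also thin. That different people test at each site is inferred from where procedures take place. The separate local laboratories process bloods and have no bearing on cognition or mood ratings. I make no claim about rater training or calibration across sites.

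A reader might infer from section 9.2 that two drug managers drew from one blocked sequence and so lost its balance. The text does not support that. It speaks of sequences in the plural and is equally compatible with one list per site, in which case site was largely balanced by design. The wording is unclear and shows no fault in conduct.

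The reply does not justify leaving site out. Baseline adjustment gives no protection against a difference that arises after baseline. If lists were per site, that is a reason to include site, because a factor used in the allocation belongs in the analysis.

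**Conclusion.** The omission is a fact of both documents: two sites, outcomes that staff administer or rate, and no site term in the stated strata or in any model. Its consequence is modest. Under the assumed shares and site differences, the standard error grows by about 1% to 8%. A 10:5 split of 15 satellite patients would move the estimate by 0.5 to 1.25 points in either direction.

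A reader might go further and conclude that site imbalance passes undiminished into the treatment contrast, or that the result would be biased. The documents do not support that: baseline is in both primary models, and the imbalance is random.

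The case for change is that adjustment costs almost nothing, gains several points of power in the least favourable scenario, and is far easier to defend if specified before the treatment codes are known. The satellite's share and every site-effect size here are assumptions, and SD 9.4 is the protocol's planning value for verbal learning.

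**What to change.** - Before unblinding, add site (two levels) as a fixed effect in the SAP's Week 8 ANCOVA and in the secondary mixed models. In any mixed model that keeps the baseline visit among the responses, enter site by visit, because a site main effect alone would absorb only a stable difference.
- Report arm-by-site counts in the baseline table.
- State whether the randomisation lists were generated per site. If they were, site is a design stratum and its place in the model follows from that. In the same paragraph, reconcile the strata in Protocol sections 3.0, 9.0 and 9.2 with the SAP's statement that stratification was amended, and say what was actually used.
- If randomisation is complete, as the SAP's past tense for treatment received suggests, no change to the lists is needed.

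The cost is a few sentences in the SAP and one degree of freedom: with 60 patients and intercept, treatment and baseline in the ANCOVA, 57 residual degrees of freedom become 56. If the sites do not differ, the loss is at most about 1 point of power. If unblinding has already taken place, give the site-adjusted result as a sensitivity analysis labelled as added afterwards.
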